### 11.3.9.3 Information to be Provided by the Investigator

SAEs must be recorded on the SAE form in the EDC system. This requirement includes all SAEs that occur after informed consent and through 28 days after study drug dosing, and in addition, any SAE that are assessed as related to study treatment by the Investigator, even if the SAE occurs more than 28 days after study drug dosing.

The minimum information required for SAE reporting includes identity of Investigator, site number, subject number, an event description, SAE term(s), onset date, the reason why the event is serious (i.e., the seriousness criteria) and the Investigator's assessment of the relationship of the event to study treatment. Additional SAE information including medications or other therapeutic measures used to treat the event, action taken with the study treatment due to the event, and the outcome/resolution of the event will be recorded. Paper forms for reporting SAEs will be provided to the study sites as back-up in case the EDC system is not accessible.

In all cases, the Investigator should continue to monitor the clinical situation and report all material facts relating to the progression or outcome of the SAE. Furthermore, the Investigator may be required to provide supplementary information as requested by Syntimmune or designee.

When reporting an SAE, the following additional points should be noted:

- When the diagnosis of an SAE is known or suspected, the Investigator should report the diagnosis or syndrome as the primary SAE term, rather than as signs or symptoms. Signs and symptoms may then be described in the event description. For example, dyspnea should not be used as an SAE term if the diagnosis, which caused the dyspnea, is known to be malignant pleural effusion.
- Death should not be reported as an SAE, but as an outcome of a specific SAE, unless the event preceding the death is unknown. In the exceptional case where the events leading to death are unknown, then death may be used as an event term. If an autopsy was performed, the autopsy report should be provided.
- While most hospitalizations necessitate reporting of an SAE, some hospitalizations do not require SAE reporting, as follows:
  - Elective or previously scheduled surgery, e.g., a previously scheduled ventral hernia repair
  - Procedures for pre-existing conditions that have not worsened after initiation of treatment
  - Pre-specified study hospitalizations for observation
  - Events that result in hospital stays of less than 24 hours and that do not require admission, e.g., an emergency room visit for hematuria that results in a diagnosis of cystitis and discharge to home on oral antibiotics
- SAEs must, however, be reported for any surgical or procedural complication resulting in prolongation of the hospitalization.

#### **11.3.10 Regulatory Reporting**

Syntimmune (or designee) will process and evaluate all SAEs as soon as the reports are received. For each SAE received, Syntimmune will decide as to whether the criteria for expedited reporting have been met.

Syntimmune (or designee) will submit SAEs that meet the criteria for expedited reporting to the regulatory authorities in accordance with local regulations governing safety reporting. Reporting of SAEs by the Investigator to his or her IRB will be done in accordance with the standard operating procedures and policies of the IRB. Adequate documentation must be maintained showing that the IRB was properly notified.

### **11.3.11 Follow-up Information on a Serious Adverse Event (SAE)**

Appropriate diagnostic tests should be performed and therapeutic measures, if indicated, should be instituted. Appropriate consultation and follow-up evaluations should be carried out until the event has returned to baseline or is otherwise explained by the Investigator.

If all required information on the SAE form is not available at the time of the initial report, follow-up information will be completed in the EDC system.

## **11.4 Other Safety Considerations**

### **11.4.1 Laboratory Data**

All laboratory data obtained during the study should be reviewed. Any abnormal value that leads to a change in subject management (e.g., requirement for additional medication or monitoring) or is of clinical significance by the Investigator should be reported as an AE and/or SAE as appropriate, unless this value is consistent with values obtained before entry into the study.

### **11.4.2 Medication Errors**

Any medication error that results in an AE, even if it does not meet the definition of serious, requires reporting within 24 hours to the safety Medical Monitor.

### **11.4.3 Follow-Up of Adverse Events**

Any SAE or AE assessed as related that led to treatment discontinuation (including clinically significant abnormal laboratory values that meet these criteria) and ongoing 28 days after study drug dosing must be followed until either resolution of the event or determination by the Investigator that the event has become stable or irreversible. This follow-up guidance also applies to related SAE that occur more than 28 days after study drug dosing. The status of all other continuing AEs will be documented as of 28 days after study drug dosing. The Investigator will follow all subjects who experience AEs until there is a return to the subject's baseline condition, or until a clinically satisfactory resolution has been achieved. The appropriate follow-up visits must be scheduled and the specific tests repeated or performed as necessary.

Where a diagnosis is possible, it is preferable to report this diagnosis rather than a series of terms (signs/symptoms) relating to the diagnosis.

### **11.5 Safety Monitoring for Dose Escalation**

Following dosing in each cohort, all safety/tolerability data (e.g., PEs, vital signs [including pulse oximetry], clinical safety laboratory tests, ECGs and AE/SAE assessments) as well as any available and relevant PD data collected through Day 42 will be reviewed by the DEC. A decision to escalate to the next cohort will be made. The recommendation may be to continue to the next scheduled dose level, discontinue the study or to modify dosing to a dose less than the current dose or higher than the current dose but lower than the next planned dose.

## 12 STATISTICAL CONSIDERATIONS

All descriptive and inferential statistical analyses will be performed using the most recently released and available Statistical Analysis System (SAS) software, unless otherwise noted. Missing data will not be imputed unless otherwise stated. All clinical data captured will be provided in data listings. A Statistical Analysis Plan (SAP) and a Pharmacokinetic Analysis Plan (PAP) will be finalized prior to database lock.

### 12.1 General Design

All data for enrolled subjects will be presented in data listings by subject number.

Continuous data will be described using descriptive statistics: number of observations (n), mean, standard deviation (SD), median, minimum, and maximum. Frequencies and percentages will be used for summarizing discrete (categorical) data. When categorical data are presented, the percent will be suppressed when the count is zero to draw attention to the non-zero counts. The denominator for all percentages, unless otherwise specified, will be the number of subjects in the specified analysis population.

### 12.2 Sample Size Justification

Formal sample size calculations were not performed. The number of subjects was chosen based on feasibility and was considered sufficient to meet the study objectives.

### 12.3 Statistical Considerations

Detailed methodology for summary and statistical analyses of the data collected in this study will be documented in a statistical analysis plan (SAP). The SAP may modify the plans outlined in the protocol; any deviations from the previously described statistical plan will be described and justified in an SAP amendment. Additional statistical analyses other than those described in this section may be performed if deemed appropriate and will be described in the SAP. Methods of handling of missing data for different endpoints will be further specified in the SAP. In general, where individual data points are missing because of insufficient samples, dropouts, or other reasons, the data will be analyzed based on reduced denominators unless specified otherwise in the SAP.

Results will be summarized by cohorts.

#### 12.3.1 Study Populations

Three populations will be employed in the analysis of study data:

- The **intent-to-treat (ITT)** population will consist of all subjects who have received at least one dose of study drug. All safety analyses will be performed on the ITT population.
- The **PK** population will consist of all subjects who receive at least one dose of study drug and have sufficient post-dose blood samples to obtain PK parameters.
- The **PD** population will consist of all subjects who receive at least one dose of study drug and have post-dose PD data available.

Primary safety analyses will be performed on the ITT population. Demographics, subject disposition, and screening and baseline characteristics will be summarized for the ITT, PK, and PD populations, where appropriate.

### **12.3.2 Subject Accountability, Demographics, and Baseline Characteristics**

Subject disposition, demographic information and baseline characteristics will be presented. Any discrepancy between treatment to be given and treatment received will be accounted for in these displays.

### **12.3.3 Concomitant Medications**

Concomitant medications will be coded using WHO Drug Dictionary (WHO-DD March 2013, Type B2 or later) and the data will be summarized and presented in tables and listings.

### **12.4 Planned PK Analysis**

Study drug concentrations will be used to calculate the following PK parameters:  $t_{1/2}$ ,  $C_{max}$ ,  $T_{max}$ , and  $AUC_{0-24}$  and  $AUC_{0-\infty}$ . PK parameters will be determined using noncompartmental method(s). Descriptive statistics of PK parameters for SYNT001 will include mean, SD, coefficient of variation (CV), median, minimum, and maximum.  $T_{max}$  will be reported as median and range. All descriptive statistics will be performed on untransformed PK parameters and after  $\log_{10}$  transformation of PK parameters.

For calculation of mean concentrations and generation of mean concentration-time profiles, all below the limit of quantification (BLQ) values will be set to zero except when an individual BLQ falls between 2 quantifiable values, in which case it will be omitted.

If there are values above the BLQ, but too sparse to allow full analysis, descriptive statistics will be performed on available values.

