### 9.1 SYNT001

SYNT001 is provided in vials containing 5 mL SYNT001 (extractable volume) at a nominal concentration of 50 mg/mL. The product is supplied as a liquid at pH  $6.5 \pm 0.5$ . SYNT001 is diluted in Dextrose 5% in Water (D5W) to prepare the solution for infusion. SYNT001 will be infused via IV in 250 mL over 1 hour using a 0.2-micron, inline filter.

Two cohorts of 8 eligible subjects each will receive 5 once-weekly 60-minute infusions of SYNT001 in planned doses of 10 mg/kg or 30 mg/kg. Based on review of safety, PD, and clinical outcomes of these two cohorts, a third cohort of up to 8 subjects may be treated at another dose, with a maximum dose of 45 mg/kg, but may also be lower than 10 mg/kg or between 10 and 30 mg/kg, inclusive.

The specification for host cell DNA in SYNT001 is  $< 2$  pg/mg, the limit of quantitation of the assay. To comply with regulatory guidelines, which specify a maximum level of 10 ng host cell DNA per dose, dosing is limited to 5000 mg of SYNT001. Therefore, at the highest dose possible in this study (45 mg/kg), maximum subject weight will be limited to 111 kg.

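### The protocol's CV of log10-transformed PK parameters depends on the unit chosen and cannot be interpreted; a geometric CV should replace it

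*Protocol*

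**What the plan says.** Section 12.4 of the protocol (Planned PK Analysis) names the summaries: "Descriptive statistics of PK parameters for SYNT001 will include mean, SD, coefficient of variation (CV), median, minimum, and maximum". It sets one parameter apart, since Tmax "will be reported as median and range". It then adds that "All descriptive statistics will be performed on untransformed PK parameters and after" log10 transformation. The statistical methods part of the synopsis gives the same list and the same two-scale rule. Neither place mentions a geometric mean or a geometric CV.

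The opening of Section 12 adds that "A Statistical Analysis Plan (SAP) and a Pharmacokinetic Analysis Plan (PAP) will be finalized prior to database lock". Neither of those plans was available for this review.

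**The concern.** The two-scale rule covers every statistic in the list, and CV is in the list. The plain reading is therefore that a CV is computed from the log10 values of Cmax, AUC0-24, AUC0-inf and half-life.

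A CV is an SD expressed as a fraction of the mean, which has meaning only on a scale with a true zero. A logarithm has none: its zero lies wherever the raw value equals one unit. The result then depends on whether a concentration is tabulated in ng/mL or mg/mL, or a half-life in hours or days.

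The most troublesome output is the one that looks plausible. A negative CV would be noticed. A small positive value labelled CV could be taken for very low between-subject variability when the real figure is several times larger. PK parameters are named secondary outcome measures (Section 4.2).

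**Working it through.** **Inputs.** From the protocol: the list of statistics and the two scales (Section 12.4 and synopsis), and cohorts of 8 subjects ("Two cohorts of 8 eligible subjects each will receive 5 once-weekly 60-minute infusions", Section 9.1). The protocol states no PK value or variability, and "Formal sample size calculations were not performed" (Section 12.2), so there is no figure of the plan's own to reproduce. The geometric means and CVs below are assumptions, with geometric CV taken over 20% to 50%.

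**Algebra.** Let y = log10(c x), where c is the unit conversion factor.

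- mean(y) = log10(c) + mean(log10 x)
- SD(y) = SD(log10 x)

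The SD does not depend on c, but the mean does. SD/mean therefore changes with the unit, is negative when the geometric mean is below 1 in that unit, and is undefined when it equals 1.

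**From geometric CV to log10 SD.** SD_log10 = sqrt(ln(1 + gCV^2)) / ln 10.

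- gCV 20%: sqrt(ln 1.04)/2.3026 = 0.0860
- gCV 30%: sqrt(ln 1.09)/2.3026 = 0.1275
- gCV 50%: sqrt(ln 1.25)/2.3026 = 0.2052

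**AUC illustration.** The geometric mean is 10,000 ug.h/mL, which is 10 mg.h/mL, or 10/24 = 0.417 mg.day/mL. The mean logs are 4.0, 1.0 and -0.380. Each entry is SD_log10 divided by the mean log.

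| Assumed geometric CV | ug.h/mL | mg.h/mL | mg.day/mL |
|---|---|---|---|
| 20% | 2.2% | 8.6% | -22.6% |
| 30% | 3.2% | 12.7% | -33.5% |
| 50% | 5.1% | 20.5% | -54.0% |

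**Other parameters, geometric CV 30%, n = 8 lognormal scores.** Cmax with geometric mean 200 ug/mL gives 2.4% in ng/mL, 5.5% in ug/mL and -18.2% in mg/mL. Half-life with geometric mean 12 h gives 11.8% in hours and -42.4% in days. With a geometric mean of 24 h, the value in days is undefined, because the mean log is zero.

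**What does not move.** In the 30% case the log10 SD stays at 0.1275 in every unit. For Cmax the untransformed CV stays at 29.3%, slightly below 30% because it is a sample value from 8 scores.

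**The unit-free alternative.** Geometric CV = sqrt(exp((ln 10 x SD_log10)^2) - 1). With SD_log10 = 0.1275, ln 10 x SD = 0.2936, its square is 0.0862, exp gives 1.09, and the square root of 0.09 is 30.0%. The same formula returns 20.0% and 50.0% from 0.0860 and 0.2052.

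**The case against.** Four points can be made for the plan.

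1. A reader might infer that all of the log-scale PK variability is meaningless, or that the trial would report no sound variability figure. The documents do not support that. The log10 SD is in the same list, is unit-free and converts exactly to a geometric CV. The log10 mean back-transforms to the geometric mean, and the minimum and maximum to the original extremes. The log-scale median is likewise sound, apart from how the two middle values are averaged when n is even. The same sentence also requires the CV of the untransformed values, which is valid in any unit. This stands: one of six log-scale statistics fails, and a sound CV sits beside it.

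2. A reader might also infer that a wrong CV would distort dose selection. Nothing in the protocol links the two. Sections 4.3, 8.4.1 and 11.5 base cohort decisions on safety, pharmacodynamic and clinical data, and Section 12.8 plans no statistical analyses to support them. This stands too.

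3. The protocol never writes the CV out as SD over mean of logs, so an analyst could derive a geometric CV from the log data. That would be sensible practice, but the text does not say it. The words name a CV and apply it to transformed values.

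4. The PK analysis plan may settle the matter, and Section 12.3 lets the SAP modify the protocol's plans. Leaving detail to those documents is normal, and silence on geometric statistics would be no fault in itself. Here, though, the protocol is not silent: it fixes both the statistic and the scale. Section 12.3 also asks for departures from the described plan to be described and justified in an SAP amendment, so the correct analysis would have to be presented as a departure.

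**Conclusion.** The point holds for the CV of the log10-transformed parameters and for nothing else. Followed literally, Section 12.4 and the synopsis produce a number that depends on the unit and can be negative or undefined. That conclusion is algebraic and needs no assumption about the drug. The sizes shown are illustrations resting on assumed geometric means and geometric CVs of 20% to 50%. The extreme values arise only when the geometric mean falls near or below 1 in the chosen unit.

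The effect is limited to one descriptive statistic for a secondary objective. The primary safety analysis, the sample size, the escalation decisions and the remaining PK summaries are untouched. Severity is low.

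**What to change.** In Section 12.4 and in the synopsis, state that for Cmax, AUC0-24, AUC0-inf and half-life the log-scale summary gives the geometric mean and the geometric CV, with geometric CV = sqrt(exp((ln 10 x SD_log10)^2) - 1), and that no CV is computed from the log values themselves. Keep the mean, SD, CV, median, minimum and maximum of the untransformed values. State that Tmax is given as median and range only, so that the two-scale rule does not appear to reach it. Carry the same definition into the PK analysis plan.

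The cost is wording in two places of the protocol. No data, visits or samples change, and the geometric CV comes directly from the log10 SD already planned.

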## **12.5 Safety Data**

Safety observations and measurements include AEs, safety laboratory tests, vital sign measurements, PEs, and ECGs.

Treatment-emergent AEs will be summarized using the Medical Dictionary for Regulatory Activities (MedDRA®; Version 19 or higher) System Organ Class (SOC) and preferred term, classified from verbatim terms. The incidence and percentage of subjects with at least 1 occurrence of a preferred term will be included, using the most severe grade. The number of events per preferred term will also be summarized. Causality (relationship to study treatment) will be summarized separately.

AEs, SAEs, and AEs leading to withdrawal, dose modification, or treatment discontinuation will be listed by subject, cohort, and overall per SOC and preferred terms. Duration of AEs will be determined and included in listings, along with action taken and outcome.

Laboratory results will be summarized by cohort. Incidence of laboratory abnormalities will be summarized. The worst on-study grade after the first dose of study drug will be summarized. Results for variables that are not coded will be presented in the listings as below, within, and above the normal limits of the local laboratory.

Vital sign measurements and change from baseline will be summarized at each scheduled time point by cohort using descriptive statistics.

Arithmetic mean of parameters from triplicate ECG will be calculated first for each participant at each planned time point. Then summary statistics of ECG test parameters (mean of triplicate) and change from baseline to each post-dose time point will be calculated. Shift tables for ECG test result category change (normal, abnormal, clinically abnormal) from pre-dose to each post-dose time point showing number and percentage of subjects with movement between categories will be presented by treatment group. Frequency and percentage of subjects experiencing potential QTc prolongation ( $QTcF > 450$ ) will be summarized at each time point by cohort.

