## 6.7 Clinical Laboratory Measurements

Collection time for all safety, PD, and exploratory labs are outlined in [Table 1](#).

Laboratory testing (hematology, urinalysis, serum chemistry, virology, serology, pregnancy tests, PD samples, PK samples, and anti-drug antibody samples) will be performed using established methods by a central laboratory. Safety laboratory panels are defined as listed in Table 3. Blood and urine samples for hematology, serum chemistry, and urinalysis will be prepared using standard procedures. Results will be provided to the Investigator. Aliquots from the PK, biomarker and anti-drug antibody samples may be retained as back-up for additional testing as necessary. Subjects will be in a seated or supine position during blood collection. Full clinical safety lab draws will be collected at Screening and on Days 0, 7, 14, 21, 28, 33, 42 and 56. The total blood draw for each subject who completes the study at Day 56, will be approximately 308 mL. Please refer to the Laboratory Manual for more information.

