**Table 3: Clinical Laboratory Panels**

Hematology	Serum Chemistry	Urinalysis

 
CBC with differential
 
Erythrocyte Sedimentation Rate (ESR)
 
	
 
Albumin
 
Alkaline phosphatase
 
ALT
 
AST
 
BUN
 
Calcium
 
Carbon dioxide
 
Chloride
 
Creatinine
 
Glucose
 
LDH
 
Phosphorus
 
Potassium
 
Sodium
 
Total and direct bilirubin
 
Total protein
 
Uric acid
 
C-Reactive Protein
 
	
 
Appearance
 
Color
 
pH
 
Specific gravity
 
Ketones
 
Protein
 
Glucose
 
Nitrite
 
Urobilinogen
 
Blood/hemoglobin
 
Leukocyte esterase
 
Bilirubin
 
Microscopic examination of sediment: only if the results of the urinalysis dipstick evaluation are positive for blood/hemoglobin
 

Virology		

 
Hepatitis C
 
Hepatitis B
 
		

- 
- HIV
  - VZV
  - Tetanus
- 

ALT = alanine aminotransferase; AST = aspartate aminotransferase; CBC = complete blood count; BUN = blood urea nitrogen; HIV = human immunodeficiency virus; LDH = lactate dehydrogenase; VZV = varicella-zoster virus

Abnormalities in clinical laboratory tests that are considered clinically significant are to be recorded on the AE electronic case report form (eCRF) page. Laboratory results will be graded using the NCI CTCAE, Version 4.03. If laboratory values constitute part of an event that meets criteria defining it as serious, the event (and associated laboratory values) must be reported as an SAE (see [Section 11.3.1](#)).

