### 6.8 Study Drug Administration

Two cohorts of 8 eligible subjects each will receive 5 once-weekly 60-minute IV infusions of SYNT001 10 mg/kg or up to 30 mg/kg. SYNT001 will be given as a 250-mL IV infusion over 1 hour using a 0.2-micron, inline filter. Based on review of safety data, as well as available and relevant PD results, and clinical outcomes of Cohort 1, a decision about proceeding with Cohort 2 will be made. Based on review of all safety data, available PD results, and clinical outcomes of these 2 cohorts, a third cohort of 8 subjects may be treated at another dose, with a maximum dose of 45 mg/kg, but may also be lower than 10 mg/kg or between 10 and 30 mg/kg, inclusive.

Cohort No.	Study Drug	Dose Level (mg/kg/dose)
1	SYNT001	10 mg/kg
2	SYNT001	30 mg/kg

See [Section 9.1](#) for dosing schedule.

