## 7 STUDY ASSESSMENTS

### 7.1 Screening Period: Day -14 to Day -1

Informed consent must be obtained before any study-specific samples are taken or study-specific tests or evaluations are conducted. The following assessments at the screening visit are to occur within 14 days before dosing. Study eligibility will be based on satisfying all the study inclusion and exclusion criteria.

At the screening visit, information will be collected and subjects will have clinical evaluations as follows:

- Informed consent ([Section 6.1](#))
- Medical history and demographic data ([Section 6.2](#))
- Review inclusion and exclusion criteria ([Section 5.2](#), [Section 5.3](#))
- Complete PE, including height and weight ([Section 6.3](#))
- Vital sign measurements (after 5 minutes of rest; sitting blood pressure, heart rate, respiratory rate, oral temperature); abnormal results to be repeated after 5 minutes of rest ([Section 6.5](#))
- 12-Lead ECG (to be obtained in triplicate after 5 minutes of rest in the supine position) ([Section 6.6](#))
- Clinical safety laboratory tests (hematology, serum chemistry panel, urinalysis) ([Section 6.7](#))
- Pregnancy test ([Section 6.7](#))
- Hepatitis and HIV screen ([Section 6.7](#))
- PD sample collection ([Section 6.7](#))
  - IgG, IgG subtypes (IgG1-4), IgA, IgM
  - Anti-Dsg (1 and 3) antibody titer
- Concomitant medication assessment ([Section 6.9](#))
- AE assessment ([Section 6.10](#))

### 7.2 Enrollment and First Treatment: Day 0

Study Day 0 is defined as the date the subject is administered their first dose of study drug. On Day 0, subjects will be asked to come to the clinic and the following procedures will be performed prior to the first dose of study drug:

- Complete physical exam ([Section 6.3](#))
- Vital sign measurements (sitting blood pressure, heart rate, respiratory rate, oral temperature); to be measured immediately prior to the infusion ([Section 6.5](#))
- Pulse oximetry (to be measured immediately prior to the infusion) ([Section 6.5](#))

- Clinical safety laboratory tests (hematology, serum chemistry panel, urinalysis) ([Section 6.7](#))
- Pregnancy test ([Section 6.7](#))
- Serum tetanus antibody and VZV antibody ([Section 6.7](#))
- PDAI Score ([Section 6.4](#))
- PK baseline sample collection (collected just prior to the start of the study drug infusion) ([Section 6.7](#))
- Immunogenicity sample collection (collected just prior to the start of study drug infusion) ([Section 6.7](#))

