## Grades

Grade refers to the severity of the AE. The CTCAE displays Grades 1 through 5 with unique clinical descriptions of severity for each AE based on this general guideline:

- Grade 1 Mild; asymptomatic or mild symptoms; clinical or diagnostic observations only; intervention not indicated.
- Grade 2 Moderate; minimal, local or noninvasive intervention indicated; limiting age-appropriate instrumental ADL\*.
- Grade 3 Severe or medically significant but not immediately life-threatening; hospitalization or prolongation of hospitalization indicated; disabling; limiting self care ADL\*\*.
- Grade 4 Life-threatening consequences; urgent intervention indicated.
- Grade 5 Death related to AE.

A Semi-colon indicates 'or' within the description of the grade.

A single dash (-) indicates a grade is not available.

Not all Grades are appropriate for all AEs. Therefore, some AEs are listed with fewer than five options for Grade selection.

## Grade 5

Grade 5 (Death) is not appropriate for some AEs and therefore is not an option.

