Carbon monoxide diffusing capacity decreased	3 - 5 units below LLN; for follow-up, a decrease of 3 - 5 units (ml/min/mm Hg) below the baseline value	6 - 8 units below LLN; for follow-up, an asymptomatic decrease of >5 - 8 units (ml/min/mm Hg) below the baseline value	Asymptomatic decrease of >8 units drop; >5 units drop along with the presence of pulmonary symptoms (e.g., >Grade 2 hypoxia or >Grade 2 or higher dyspnea)	-	-
Definition: A finding based on lung function test results that indicate a decrease in the lung capacity to absorb carbon monoxide.					
Cardiac troponin I increased	Levels above the upper limit of normal and below the level of myocardial infarction as defined by the manufacturer	-	Levels consistent with myocardial infarction as defined by the manufacturer	-	-
Definition: A laboratory test result which indicates increased levels of cardiac troponin I in a biological specimen.					
Cardiac troponin T increased	Levels above the upper limit of normal and below the level of myocardial infarction as defined by the manufacturer	-	Levels consistent with myocardial infarction as defined by the manufacturer	-	-
Definition: A laboratory test result which indicates increased levels of cardiac troponin T in a biological specimen.					
CD4 lymphocytes decreased	<LLN - 500/mm  ; <LLN - 0.5 x 10  /L	<500 - 200/mm  ; <0.5 - 0.2 x 10  /L	<200 - 50/mm  ; <0.2 x 0.05 - 10  /L	<50/mm  ; <0.05 x 10  /L	-
Definition: A finding based on laboratory test results that indicate a decrease in levels of CD4 lymphocytes in a blood specimen.					
Cholesterol high	>ULN - 300 mg/dL; >ULN - 7.75 mmol/L	>300 - 400 mg/dL; >7.75 - 10.34 mmol/L	>400 - 500 mg/dL; >10.34 - 12.92 mmol/L	>500 mg/dL; >12.92 mmol/L	-
Definition: A finding based on laboratory test results that indicate higher than normal levels of cholesterol in a blood specimen.					
CPK increased	>ULN - 2.5 x ULN	>2.5 x ULN - 5 x ULN	>5 x ULN - 10 x ULN	>10 x ULN	-
Definition: A finding based on laboratory test results that indicate an increase in levels of creatine phosphokinase in a blood specimen.					

Investigations					
Adverse Event	Grade				
	1	2	3	4	5
Creatinine increased	>1 - 1.5 x baseline; >ULN - 1.5 x ULN	>1.5 - 3.0 x baseline; >1.5 - 3.0 x ULN	>3.0 baseline; >3.0 - 6.0 x ULN	>6.0 x ULN	-

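### Creatinine graded by CTCAE 4.03 as written puts about 7 of 8 subjects per cohort in Grade 1 with no drug effect, so the Grade 1 creatinine count is uninformative

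*Protocol*

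**What the plan says.** Protocol Section 6.7, below Table 3, sets the scale: "Laboratory results will be graded using the NCI CTCAE, Version 4.03". No analyte is excepted, and creatinine is in the Table 3 chemistry panel.

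Appendix A reproduces the scale. Under Investigations, Grade 1 for raised creatinine is ">1 - 1.5 x baseline; >ULN - 1.5 x ULN", and the notes on grades state: "A Semi-colon indicates 'or' within the description of the grade". The baseline criterion therefore suffices by itself.

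The sampling schedule in Section 6.7 is: "Full clinical safety lab draws will be collected at Screening and on Days 0, 7, 14, 21, 28, 33, 42 and 56". Section 7.2 places the Day 0 safety laboratory tests among the pre-dose procedures ("the following procedures will be performed prior to the first dose of study drug"). That leaves one Day 0 value and seven later ones.

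Section 12.5 fixes the summary: "The worst on-study grade after the first dose of study drug will be summarized". It also calls for the incidence of laboratory abnormalities, without saying whether this is built from grades. It gives no special rule for creatinine and plans no change-from-baseline display for laboratory results. Change from baseline is specified only for vital signs and ECG, and the one shift table described is for ECG.

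Section 6.8 gives the cohort size: "Two cohorts of 8 eligible subjects each will receive 5 once-weekly 60-minute IV infusions".

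**The concern.** Read literally, the criterion has no minimum change. A move from 0.80 to 0.81 mg/dL, well within ordinary measurement variation, is Grade 1. Taking the worst grade over seven draws gives each subject seven chances to exceed a single reference value.

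Neighbouring entries in Appendix A do not behave this way. Grade 1 for ALT, AST, alkaline phosphatase and bilirubin needs a value above ULN. Grade 1 acute kidney injury needs a creatinine rise of more than 0.3 mg/dL or 1.5 to 2.0 times baseline. One row of the laboratory table would thus mean something different from the rows beside it.

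At stake is the readability of part of the primary safety evidence. Clinical laboratory tests belong to the primary outcome in Section 4.2, and with no control group there is no comparator row in which the same excess would appear and reveal itself as noise.

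**Working it through.** The protocol states no figure to reproduce. The study is descriptive (Section 12.2: "Formal sample size calculations were not performed"), so the check asks what the worst-grade rule yields when the drug does nothing.

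**Inputs from the protocol.** k = 7 post-dose draws (Days 7, 14, 21, 28, 33, 42, 56); one pre-dose Day 0 value; n = 8 per cohort; Grade 1 if any post-dose value exceeds baseline.

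**Exact rank argument.** With no drug effect and no trend, the eight values of one subject are exchangeable. The subject avoids Grade 1 by the baseline criterion only if Day 0 is the largest:

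- P(Grade 1 or higher) = k/(k + 1) = 7/8 = 0.875
- expected count = 8 x 0.875 = 7.0 of 8
- P(all 8) = 0.875^8 = 0.344
- P(at least 7 of 8) = 0.875^7 + 0.875^8 = 0.393 + 0.344 = 0.736

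Missing visits matter little: six post-dose draws give 6/7 (6.9 of 8) and five give 5/6 (6.7 of 8).

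**Sensitivity (simulation).** The protocol gives neither the reporting precision nor the within-subject variation, and Section 12.5 does not say which value is the laboratory baseline. Assumed here: subject means of 0.6 to 1.1 mg/dL and within-subject CV of 3 to 8%. Expected subjects of 8 with Grade 1 or higher and no drug effect:

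| Baseline | Unrounded | Reported to 0.01 mg/dL | Reported to 0.1 mg/dL |
|---|---|---|---|
| Day 0 | 7.0 | 6.7 to 6.9 | 2.9 to 5.5 |
| Mean of screening and Day 0 | 7.4 | 7.3 to 7.4 | 3.9 to 6.6 |
| Higher of screening and Day 0 | 6.2 | 5.7 to 6.0 | 1.9 to 4.1 |

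The unrounded value in the last row also follows by rank: 7/9 x 8 = 6.2. Coarse reporting lowers the count because ties with baseline are not rises. Serial correlation of 0.3 or 0.6 (Day 0 baseline, unrounded) gives 0.862 or 0.843 per subject, that is 6.9 or 6.7 of 8.

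**Higher grades.** The chance that any post-dose value exceeds 1.5 x baseline is below 0.5% per subject in every scenario. The excess is confined to Grade 1.

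**With the ULN criterion only for Grade 1** (assumed ULN 1.2 mg/dL, other assumptions as above, Day 0 baseline): the per-subject rate is 0 to 0.055, or at most 8 x 0.055 = 0.44 of 8. Keeping the multiple above 1.5 x baseline adds at most 8 x 0.005 = 0.04. The expected false count falls from about 7 of 8 to below 0.5 of 8.

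**The case against.** The strongest reply is that this belongs to the SAP. Section 12.3 sends detailed methods there and lets the SAP modify the protocol's plan; the SAP is not shown; and the protocol quotes a published scale correctly. That would settle the matter if the protocol were silent. It is not: it names the scale, reproduces the criterion and fixes the worst-grade summary, and following it as written produces the excess. The choice of laboratory baseline, by contrast, can properly be left to the SAP and is treated here only as an assumption.

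Three stronger readings are tempting and are not supported:

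- **That a real renal signal would be hidden.** A worst-grade table separates the grades. Chance entries at Grade 2 or higher are rare, so a substantial rise would stand out. The synopsis has laboratory results summarized by time point and cohort, and Section 12 lists all clinical data, so with 8 subjects each series can be read directly. What is lost is the ability to tell a modest rise from noise within Grade 1.
- **That dose escalation is affected.** The rule in Section 8.4.1 turns on Grade 3 events judged clinically significant and drug related, in at least 2 subjects. Spurious Grade 1 values cannot meet it, and Section 12.8 plans no statistical analysis for these decisions.
- **That the adverse event tables would show creatinine toxicity.** Sections 6.7 and 11.4.1 send laboratory findings to the adverse event record when they are clinically significant or change management. A trivial rise within the normal range would not normally qualify.

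The objection that a ULN-only Grade 1 could remove the only planned graded display of within-range rises is correct. The remedy has to replace that display.

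**Conclusion.** The point holds in limited form. Applied as written, the plan makes the Grade 1 creatinine count uninformative, along with any laboratory abnormality incidence that is built from grades. About 7 of 8 subjects per cohort are expected to qualify with no drug effect, given a single Day 0 baseline, complete visits and values reported finely enough that ties are rare. At 0.1 mg/dL reporting the expectation is about 3 to 5.5 of 8 with the same baseline. A reader might take 7 of 8 as a ceiling or as a certainty; it is an expectation, and all 8 subjects qualify with probability 0.34 under the same assumptions.

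The mechanism rests on the protocol's own text. The exact rate rests on reporting precision, within-subject variation and choice of baseline, none of which the protocol states. Grade 2 or higher, the Grade 3 stopping rule and the adverse event tables are not materially affected. A table of shifts from baseline grade to worst grade would not cure the problem, because a subject's own baseline is Grade 0 unless it exceeds ULN. The change is worth making because it is cheap and the laboratory tables serve the primary objective.

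**What to change.** State in Section 12.5 that, for the laboratory summary tables, creatinine Grade 1 is assigned on the ULN criterion only (above ULN up to 1.5 x ULN), and that the baseline multiple counts from above 1.5 x baseline upward. Leave the other grades as published.

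Add a summary of creatinine change, or ratio, from baseline by visit and cohort, including each subject's maximum post-dose value. This keeps within-range rises of up to 1.5 x baseline visible.

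The cost is a sentence, a programming rule and one extra table. The downside is a small departure from the published scale: a within-range rise to 1.49 x baseline would be ungraded, while 1.51 x would be Grade 2. A footnote to the table should say so. The change concerns tabulation only and alters no clinical rule.
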